### **Statistical Analyses**

*General Statistical Considerations.* Significance will be defined at  $\alpha = .05$ , with a cluster-determining threshold (CDT) of  $p < .001$ , as determined by Monte Carlo simulations (3dClustSim; [afni.nimh.nih.gov/pub/dist/doc/program\\_help/3dClustSim.htm](http://afni.nimh.nih.gov/pub/dist/doc/program_help/3dClustSim.htm), May 2016). Specifically, 3dcalc will take the square root of the SPM model's error variance image (ResMS) and 3dFWHMx used to empirically determine the spatial smoothness of residual error in the model using the newly developed non-Gaussian autocorrelation function (ACF). Data from the NIH, replicating the Beijing datasets [19], show that these settings, combined with CDT of  $p < .001$  and a (10mm) smoothing kernel, maintain a true false-positive rate of 5% for regular event-related designs[20].

*Experimental Inhibitory Control (IC) Task.* Data from each fMRI scan will be entered into a 1st level, whole-brain analysis using the GLM[18] to examine BOLD response to each of the 5 trial types: NoGocorrect (IC), NoGoincorrect (error of commission), RareGocorrect (correct novel-target detection), RareGoincorrect (novel-target error of omission), and Goincorrect (error of omission). Each event type will be modeled as a delta regressor at the onset of the event and convolved with a canonical hemodynamic response function. Intra-run motion will be removed through rigid body rotation and translation and parameters included as covariates. A high-pass filter (.008 Hz) will be applied to remove slow signal drift. Finally, in order to examine successful inhibitory control (IC)-related BOLD response, controlling for novelty detection, a NoGocorrect - RareGocorrect contrast image will be generated (henceforth, IC) and used for hypothesis testing. This is to be distinguished from IC accuracy, which refers to the percent of correct 'NoGo' trials achieved. Main effects of condition (iTBS vs. cTBS) on IC will be assessed via ANCOVA. Next, mean percent signal change (PSC) from 1st level models during IC will be extracted (via MARSBAR) from each of ROI within the ICN mask (Fig 4).

[figure not shown]

Figure 4: IC mask includes right inferior frontal gyrus (IFG), left precentral gyrus (BA4/M1), and bilateral thalamus (Thal), subthalamic nucleus (STN), and pre-supplementary motor area (preSMA).

***Task-based Functional Connectivity (tbFC).*** Corticothalamic tbFC will be assessed at the 2nd level based on 1st level voxel-wise bivariate correlation maps (i.e., Fisher transformed correlation coefficient [rZ-value] maps) [21].

### **VIII. Potential Risks/Adverse Events**

The main study procedures include completion of questionnaires, MRI, and TMS, all of which are generally considered minimal risk procedures. The primary risks are described below:

1. **Magnetic Resonance Imaging.** Because the MRI machine acts like a large magnet, it could move metallic objects in the MRI room during the examination, which could be harmful to the participant. To prevent such an event from happening; loose metal objects, like pocket knives or key chains, are not allowed in the MRI room. If a participant has a piece of metal in their body, such as a fragment in their eye, aneurysm clips, ear implants, spinal nerve stimulators, or a pacemaker, they will not be allowed into the MRI room and cannot have a MRI. Having a MRI may be uncomfortable, particularly regarding feelings of claustrophobia and the loud banging noise during the scan. Participants will be asked to wear earplugs to avoid possible hearing impairment.
2. **Transcranial Magnetic Stimulation:**
  - a. **Investigational Device Exemption:** Transcranial Magnetic Stimulation is an investigational device. It is a 510K/Pre-market Notification device (a device that is substantially equivalent to a legally marketed device), as described in 21 CFR 807 Subpart E.
  - b. **Potential Risks of TMS**
    - i. *Potential risk of a seizure:* The major risk using repetitive TMS subjects is the possibility of inducing a seizure. We have now studied and given rTMS to more than several hundred subjects over past 15 years. None of these patients has developed a seizure. We will exclude patients with a prior history of seizures.
    - ii. *Potential for scalp discomfort and headaches:* Some people report mild discomfort when the magnetic pulses are applied over the scalp. A small number of people (~5%) report headache following TMS. However, the headaches are temporary and manageable with common over-the-counter pain remedies.
    - iii. *Potential hearing loss:* The discharge of the rTMS coil generates a high-energy click that may cause cochlear damage. Foam earplugs can protect against these changes and will be worn by the subjects and the researchers present during TMS sessions.
3. **Incidental Findings: Magnetic Resonance Imaging:** Some MRI scans can detect medical conditions, such as cancer, brain injury, and abnormal blood vessels; however, this functional MRI is carried out purely for experimental purposes and we are not looking for brain disorders. Furthermore, the study researchers are not trained in diagnosing brain disorders; therefore, the researchers are not qualified to offer any medical opinions concerning the scan (good or bad). It is possible that the study researchers will notice something in a participant's scan that appears unusual and/or abnormal, if this occurs, the researchers will inform the participant of the finding and provide them with a copy of their scan, which they may take to

a medical expert for further review and diagnosis. Being told about such a finding may cause anxiety as well as suggest the need for additional tests and financial costs. Any costs associated with clinical follow-up(s) are the participant's and/or the participant's insurance carrier's responsibility. Participants who do not wish to be informed of such findings will be advised to not participate in this study.

4. **Breach of confidentiality:** There is the potential risk of breach of confidentiality of clinical and laboratory information. [name] has experience as an investigator dealing with such sensitive information and has experience assuring that data is adequately protected. Safeguards to protect confidentiality include locked records and firewalls around password-protected electronic data, and all study data being coded, with the key linking the code with a participant's identity being kept on secure network storage as a password protected document. Similar safeguards are followed for storage and processing of MRI data. MRI data is stored on secure network storage maintained by MU, where the PI has dual appointment. The MRI scans are identified only by subject code, study code, and date of acquisition. Participants' initials will also be present on some questionnaires; however, the questionnaires containing the initials will be stored in a locked file cabinet.

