### **Assessments, biomarkers, and self-report measures.**

- Diagnostic Assessment. A medical history and fMRI safety screening questionnaire will be conducted to ensure that the individual is eligible to participate.
- Smoking history, behavior and dependence. The following validated measures of nicotine dependence and urge to smoke will be used at various times during the study: Shiffman/Jarvik Withdrawal scale [55], Fagerström Test of Nicotine Dependence [56] & Modified Cigarette Evaluation Questionnaire [57].
- Tobacco use biomarkers. Expired air CO concentrations will be measured at screening to establish eligibility ( $CO > 10$ ) at baseline, and smoking or abstinence ( $CO < 6$ ) status prior to each experimental session, using standard procedures [33, 34]. Urinary cotinine will be used to assess quantitative measures of smoking and abstinence ( $ABS < 80$  ng/ml).
- Smoking topography. Clinical Research Support System (CReSS) Lab smoking topography device (Plowshare Technologies) will be used to assess smoking topography. Measures to be evaluated include number of puffs, puff volume (milliliters), puff duration (milliseconds), puff velocity (milliliters/second) and inter-puff interval (seconds).
- Trait and State Measures. Impulsiveness will be measured with the BIS-11 [58]. Mood state will be evaluated with the Profile of Mood States [59], which has been shown to reliably characterize the effects of abstinence on mood in dependent smokers [60, 61].
- EMA measures. Over the course of the study, participants will be prompted each day, via text messaging, to provide craving, mood ratings and quantify smoking (# cigs.) for the day through a link to a secure REDCap questionnaire and daily log of cigarettes smoked that day (see [50, 54]).
- Safety Assessment. Tolerability will be assessed using a sixteen-item review of systems (ROS) questionnaire [36] and reviewed with research team at weekly visits.

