**GoGo/NoGo Inhibitory control (IC) Task.** The “GoGo/NoGo” task [4, 44] will serve as the experimental probe to evaluate the mechanistic underpinning of TBS on IC, determine whether or not to proceed from the UG3 mechanistic proof-of-concept project to the fully-powered UH3 phase. fMRI BOLD response will be collected from participants as they perform the task. Participants are instructed to press a button in response to common (gray colored circles: 75% of trials) and rare (yellow colored circles: 12.5% of trials) Go stimuli and inhibit responding to rare NoGo stimuli (blue colored circles: 12.5% of trials). The task provides errors of omission and reaction times during Go trials, controls for novelty detection during processing of rare Go trials (yellow circles) and errors of commission on NoGo trials (blue circles). Behavioral data will be processed and analyzed consistent with our prior work with this task [4]. Prior to analysis, NoGo performance will be corrected by scoring NoGo trials with null response as incorrect when the participant did not respond to the ‘Go’ trial preceding it, in order to control for lapses in attention. Data will then be analyzed in SPSS.

**Smoking Relapse analog Task (SRT).** The SRT was developed by the PI ([name]) and smoking behavior outcomes (time to lapse) shown to be predicted by IC corticothalamic neural-circuitry function [4]. In brief, the SRT is comprised of two phases. The first involves up to 10, six-minute

blocks of randomly presented trials of neutral, smoking and emotional images. Following each block, participants rate their craving on a scale from 1-10 and then choose to earn \$1 for each additional block up to 60 min., or quit the task and smoke a cigarette using a pocket CReSS system in which topography measures are recorded.

[figure not shown]
**Neuroimaging Protocol.** Imaging will be performed on a 3T Siemens Prisma scanner: a high-resolution 3D MPRAGE anatomical sequence will be acquired (matrix = 256, flip angle = 9°, 166 slices, slice thickness = 1 mm); whole brain BOLD contrast sensitive images will be acquired using a multi-band (6) EPI sequence (60 slices, TR=800 ms, TE=30 ms, FOV=216, 2.4 mm^3 voxels). Prior to the acquisition of images, the anterior and posterior commissures will be identified in the mid-sagittal slice of a localizer series, followed by the acquisition of PA and AP field maps, and then followed the acquisition of functional images during the IC task.

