**Aim 3.** Examine safety and tolerability of administering r.IFG TBS. **Rationale.** Though TBS has a good safety profile [36, 37], prior studies assessment of tolerability and adverse events (AE's) have largely confined those assessments to the day of study [37]. In addition, although the TBS stimulation parameters proposed herein are published standards, the location—r.IFG for iTBS is novel and thus both acute and protracted (24 hrs. post-stimulation) safety and tolerability profiles need to be assessed. **Hypothesis 3:** r.IFG TBS will have a similar overall adverse event profile in a TUD population as previously observed in dorsolateral prefrontal cortex TMS trials. **Assessment Plan.** Participants will be administered the ROS questionnaire (see C.9) at the beginning and end of each TBS visit, and 24hrs. post TBS. [name] will oversee participant compliance and, in the event of an AE, consult with [name] who will serve as the Program Manager for AEs. Any AEs will be recorded in an AE log. If an AE is non-serious (self-limited with no intervention needed), no further action will be necessary. However, in the case of a serious, unresolved event, an AE follow-up log will be completed and subsequent safety procedures followed (see Human Subjects Section; DSMP). Treatment-emergent AEs for all participants and

comparisons between the number of participants with any adverse events will be conducted using Pearson's chi-squared test statistic.

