*fMRI Scan:* 1) a high-resolution anatomical scan; 2) a 7-minute run of the IC task (see Fig 1); and 3) a six minute resting state BOLD (blood-oxygen-level-dependent).

*Randomization:* This will be a single blind study where participants will be randomized 1:1 to receive one session of either intermittent TBS (iTBS) or continuous TBS (cTBS) following the first fMRI.

*SRT:* The Smoking Relapse task will be administered as described above.

*Experimental Visits 1 & 2:* At the beginning of each of these experimental visits, participants will first: provide an expired breath CO sample in order to assess recent smoking; and, among females, provide a urine sample in which the pregnancy test must be negative. Next, breath alcohol levels will be assessed with a handheld breathalyzer and participants must record a BAL of 0.0. If participants continue to be eligible after the biological samples, they will complete study questionnaires to assess mood and to characterize smoking-related behavior. After this, participants will move on to the first of two fMRI sessions followed by the TMS session and the second the fMRI and SRT task.

*fMRI Scan 1:* 1) a high-resolution anatomical scan; 2) a 7-minute run of the IC task (see Fig 1); and 3) a six minute resting state BOLD (blood-oxygen-level-dependent).

*TMS:* Upon randomization, participants will receive either iTBS or cTBS per the theta burst protocols described above.

*fMRI Scan 2:* 1) a high-resolution anatomical scan; 2) a 7-minute run of the IC task (see Fig 1); and 3) a six minute resting state BOLD (blood-oxygen-level-dependent). The second

*SRT:* The Smoking Relapse task will be administered as described above.

**Analytic Strategy** Behavioral and neural data analysis strategies are found in [1] and detailed below.

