## **XII. Data Safety Monitoring Plan**

This UG3 phase is a proof-of-concept study to test mechanistic hypotheses of the acute effects of theta bursts stimulation (TBS) on corticothalamic inhibitory control (IC) task-based functional connectivity (tbFC), IC task performance and ad lib smoking in the laboratory (smoking relapse task: SRT [4]), and while preliminarily evaluating safety and tolerability of TBS among individuals with TUD. Adults smokers meeting criteria for TUD (N =40) will complete a baseline MRI visit and, using a crossover design, be randomly assigned to receive iTBS on one visit and cTBS on the other visit. Following TBS, they will repeat the MRI protocol and then perform the SRT. The effects of TBS on IC brain and behavior and smoking on the SRT, along with safety and tolerability during each visit will be assessed.

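### Aim 3 has no tolerability rating at a fixed time right after stimulation; the only same-day ROS after TBS follows a second scan and a smoking task whose length is the Aim 2 outcome

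*Combined protocol and SAP*

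**What the plan says.** All sections cited are in the combined protocol and SAP.

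- **The expected symptom** (Section VIII, potential risks of TMS): "Some people report mild discomfort when the magnetic pulses are applied over the scalp".
- **When the ROS is given** (Section VII, Aim 3, Assessment Plan): "Participants will be administered the ROS questionnaire (see C.9) at the beginning and end of each TBS visit, and 24hrs. post TBS". The same paragraph says that any adverse event goes into an AE log, and that both the acute profile and the profile at 24 hours need assessing because the r.IFG site is new for iTBS.
- **The instrument** (Section VII, assessments list): "Tolerability will be assessed using a sixteen-item review of systems (ROS) questionnaire [36] and reviewed with research team at weekly visits". The period that the form asks about is not stated.
- **Order of the TBS visits** (Section VII, Experimental Visits 1 & 2): "participants will move on to the first of two fMRI sessions followed by the TMS session and the second the fMRI and SRT task". No symptom rating between the TMS session and Scan 2 is described.
- **The SRT** (Section VII): up to ten six-minute blocks. After each block the participant either continues for $1 or may "quit the task and smoke a cigarette using a pocket CReSS system".
- **Aim 2**: the outcome is time to start smoking on the SRT. Hypothesis 2 expects it to be longer after iTBS and shorter after cTBS.
- **Aim 3 comparison**: Hypothesis 3 compares r.IFG TBS with earlier dorsolateral prefrontal TMS trials. A Pearson chi-squared test on the number of participants with any adverse event is also planned; the groups are not named.
- **Section XII** repeats the intent: "smoking on the SRT, along with safety and tolerability during each visit will be assessed".

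**The concern.** The 24-hour form serves the protracted profile, so the end-of-visit form is the only scheduled measure of the acute one. Three features weaken it for that purpose.

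1. **Lag.** The form is given well after stimulation, while Section VIII describes scalp discomfort as felt during the pulses and headaches as temporary. Short-lived symptoms may be gone or forgotten.
2. **Attribution.** Between the last pulse and the form the participant has a further MRI, which Section VIII itself describes as potentially uncomfortable and noisy, then blocks of emotional and smoking images, and possibly a cigarette. A symptom new at the end of the visit cannot be assigned to TBS with confidence.
3. **Lag tied to an outcome.** The participant decides how long the SRT lasts, and that duration is the Aim 2 endpoint. It is determined after randomisation, so randomisation does not balance it. If Hypothesis 2 is true, iTBS symptoms would be asked about later than cTBS symptoms.

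At stake is how far the acute tolerability data can be relied on. Under-recording would make r.IFG TBS look more benign against the earlier trials, and an unequal lag could make iTBS look better tolerated than cTBS when it is not.

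**Working it through.** **Step 1. The plan's own figure.** SRT maximum = 10 blocks × 6 min = 60 min, as stated. It agrees with Section X: 10 × $1 = $10 per visit, × 3 visits = $30. SRT minimum = 1 block = 6 min.

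**Step 2. Lag from TBS to the end-of-visit ROS.** Lag = timed Scan 2 runs + SRT time.
- Timed Scan 2 runs: 7 min IC task + 6 min rest = 13 min.
- Shortest: 13 + 6 = 19 min. Longest: 13 + 60 = 73 min. The SRT alone accounts for a spread of 54 min.
- These are lower bounds. The anatomical scan, set-up and smoking time have no stated length.
- The spectroscopy sequences take (320 × 2 s + 128 × 2 s) / 60 = 14.9 min. Their position relative to TBS is not stated. If they follow TBS, the range is about 34 to 88 min.

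**Step 3. How much could be lost?** The documents give no decay rate. Assume that the form asks only about current symptoms and that discomfort fades exponentially. Share still present = 0.5^(lag / half-life).

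| Assumed half-life | Lag 19 min | Lag 73 min |
|---|---|---|
| 10 min | 27% | 1% |
| 20 min | 52% | 8% |
| 40 min | 72% | 28% |

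**Step 4. How unequal could the two conditions look?** Reported rate = p × 2^(−(13 + SRT time) / half-life), with the same true rate p in both conditions. Take p = 20% and a half-life of 30 min (both assumed).

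| SRT time, iTBS vs cTBS | Reported, iTBS | Reported, cTBS | Difference | Participants out of 30 |
|---|---|---|---|---|
| 30 vs 30 min | 7.4% | 7.4% | 0 | 0 |
| 40 vs 30 min | 5.9% | 7.4% | 1.5 points | 0.5 |
| 60 vs 20 min | 3.7% | 9.3% | 5.6 points | 1.7 |

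The range tried was p from 5% to 40%, half-lives from 10 to 120 min, and the two unequal SRT pairs above. Over it, the spurious difference runs from about 0.1 point (p = 5%, half-life 10 min, 40 vs 30 min) to about 11 points (p = 40%, half-life 30 min, 60 vs 20 min).

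With 30 per condition, treated as independent groups, the chance of p < .05 in that direction is about 3% to 25%. With no difference at all this calculation gives 2.5%, so the lower end is essentially the background rate. The normal approximation is also rough at such small counts.

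**Step 5. What removes the loss.** If the form asks about symptoms since stimulation and participants recall them, or if discomfort is volunteered and entered in the AE log, the figures in Steps 3 and 4 shrink and could be near zero. The attribution problem needs no decay or recall assumption.

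**The case against.** The other side has a good case on several counts.

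- **Other capture exists.** There is a 24-hour ROS, an AE log not tied to the ROS times, and close staff supervision (Section VIII, protection against risk). Discomfort voiced during stimulation has a route into the record. This stands, but no prompted question right after TBS feeds the log, and a form at 24 hours is poorly placed for brief discomfort.
- **A reader might infer that transient discomfort is largely missed.** The documents do not support this. The recall window is unstated, and remembering something from 19 to 73 minutes earlier is not demanding. Headache after TMS, the only such symptom given a rate (about 5%), can be picked up at the end of the visit and at 24 hours.
- **A reader might infer that the iTBS-versus-cTBS comparison is biased.** That needs Hypothesis 2 to be true, the visit to end with the SRT, and reporting to fall with lag. The SRT is said to have two phases, but the current text clearly describes only the first. It does not say how long the second lasts or whether those who complete all ten blocks also smoke. A fixed total stay would break the link in timing. The between-condition contrast is itself only the natural reading of the chi-squared sentence, since the comparator in Hypothesis 3 is external.
- **A reader might also infer that unequal discomfort (190 s versus 34 s of stimulation) contributes to the Aim 1 contrast.** Nothing in the documents shows this.
- **The decay model is assumed**, and in most cases tried the absolute difference is small.

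These objections limit the claim to what may happen. They do not supply a fixed-time acute measure, and they leave the mixing of exposures unanswered.

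**Conclusion.** The point holds as a measurement gap, not as a demonstrated bias. The visit order and block lengths establish that the only scheduled same-day ROS after stimulation has no fixed lag, comes at least about 19 to 73 minutes after TBS, and follows another MRI, the SRT and possibly a cigarette.

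Under-recording of brief discomfort is possible and depends on the unstated recall window. It would affect the comparison with earlier dorsolateral prefrontal trials as well as any comparison between conditions. Distortion between iTBS and cTBS is possible if Hypothesis 2 is true and the visit ends with the SRT. Its size cannot be derived from the documents. Under the assumptions shown it is probably modest, often less than one or two participants out of 30. The point does not threaten the trial, but an immediate rating that was never taken cannot be recovered afterwards.

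**What to change.** In the Aim 3 assessment plan, add one administration of the ROS, or at least its scalp discomfort, pain and headache items, at a fixed time immediately after the last TBS pulse and before Scan 2. Make the change from the start of the visit to this point the acute tolerability measure. Keep the end-of-visit and 24-hour forms as later time points. In the same edit, state the period that the ROS asks about and name the groups that the chi-squared test compares.

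The new measure no longer depends on SRT time and is free of the second scan, the task and any cigarette smoked in it. The change from the start of the visit still spans Scan 1, but that scan is the same in both conditions.

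Cost: one line in the schedule and one more completion of a 16-item form already in use. Scan 2 starts about one to two minutes later, equally in both conditions.
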